4.4. End of Study Definition

Part 1

A participant is considered to have completed the study if he/she has completed all visits of the study through to Day 60 or has died prior to Day 60. The end of the study is defined as the date of the last contact of the last participant in Part 2 of the study.

Part 2

A participant is considered to have completed the study if he/she has completed all visits of the study through to Day 60 or has died prior to Day 60. The end of the study is defined as the date of the last contact of the last participant in this additional cohort in Part 2 (or any future additional cohorts) in the study.

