4.4.1.4. Alive and Not Invasively Mechanically Ventilated

Participants will meet the endpoint if they are alive and not requiring invasive mechanical ventilation at Day 7, 14, 28, 42 and 60. This will be evaluated only for participants supported using invasive mechanical ventilation at baseline. This will be derived from the worst-case ventilation record as detailed in Section 6.3.2.1.

4.4.1.5. Time to Definitive Extubation up to Day 28

For participants supported using invasive mechanical ventilation at baseline this is defined as the time from dosing (days) to final extubation from invasive mechanical ventilation up to (and including) Day 28. This will be derived from the worst-case ventilation record as detailed in Section 6.3.2.1.

This endpoint will use a composite approach for death such that if the event intercurrent event of death (on or prior to Day 28) occurs, then time will be censored at the end of follow-up (Day 28), including those that were extubated prior to death.

4.4.1.6. Oxygen-free Days up to Day 28

A participant is considered oxygen free on a day if they are not using oxygen (Ventilation=None) as derived from the worst case ventilation record on a day as detailed in Section 6.3.2.1.

Intermittent data is expected after discharge from investigator site, therefore if participants have discontinued oxygen and have been discharged to a non-hospitalized residence, they will be considered to be oxygen-free during the intermittent timepoints.

4.4.1.7. Ventilator-free Days up to Day 28

A participant is considered ventilator-free on a day if they are not using invasive mechanical ventilation as derived from the worst case ventilation record on a day as detailed in Section 6.3.2.1.

Intermittent data is expected after discharge from investigator site, therefore if participants have discontinued ventilation and have been discharged to a non-hospitalized residence, they will be considered to be ventilation-free during the intermittent timepoints.

4.4.1.8. Admission to ICU up to Day 28

Participants will meet the endpoint if they have been admitted to the ICU at any point up to (and including) Day 28, only evaluated for participants not in ICU at time of dosing.

Participants who die prior to Day 28 without being admitted ICU will be considered to have met the endpoint (composite estimands strategy).

4.4.1.9. Change from Baseline in Inspired Oxygen (FiO₂) up to Day 28

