6.3.2. Derived and Transformed Efficacy Data

6.3.2.1. Ventilation Status

Ventilation status as shown below, will be derived for Days 1-60 based on the log-based collection (start and end dates/time).

Code	Decode
1	None
2	Low flow oxygen therapy
3	High-flow oxygen therapy (>= 15 L/min)
4	Non-invasive mechanical ventilation
5	Invasive mechanical ventilation
6	Death
99	Other

Ventilation status at baseline is defined as the ventilation status at the time of dosing, if no ventilation is recorded then the last ventilation use will be assigned to baseline. If multiple ventilation types are being used at the start of baseline the worst case is assumed.

For post-baseline the worst-case ventilation on a day will be used, Other will only be considered worst-case if no other ventilation is recorded.

Ventilation statuses with missing end-dates will be assumed ongoing.

Ventilation status will only be missing after last contact for subjects who have withdrawn from the trial, such that participants with no open ventilation logs will be assumed to have Ventilation=None.

Other will not be included in figures

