6.3.2.2. Clinical Status Ordinal Scale

Additional derivation of clinical status will be performed. If subject dies then their clinical status will be recorded as 8-Death from date of death to Day 60 inclusive, this will override any collected clinical status.

Otherwise if clinical status is missing and the assessment day is prior to last contact with participant, then the following rules will apply:

Category	Rule
8 - DEATH	Date of death <= date of assessment
7 - HOSPITALIZED, MECHANICAL VENTILATION+ADDITIONAL ORGAN SUPPORT	Ventilation = "INVASIVE MECHANICAL VENTILATION" and additional support includes: "EXTRACORPOREAL MEMBRANE OXYGENATION" "RENAL REPLACEMENT THERAPY (RRT)/DIALYSIS" "INOTROPES/VASOPRESSORS"
6 - HOSPITALIZED, INTUBATION AND MECHANICAL VENTILATION	Ventilation = "INVASIVE MECHANICAL VENTILATION" and does not meet the classification for additional organ support

Category	Rule
5 - HOSPITALIZED, HIGH-FLOW OXYGEN(\geq 15L/MIN), CPAP, BIPAP, NIV	Ventilation is: "NON-INVASIVE MECHANICAL VENTILATION" or "HIGH-FLOW OXYGEN THERAPY (\geq 15 L/MIN)"
4 - HOSPITALIZED, LOW-FLOW OXYGEN BY MASK OR NASAL PRONGS	Ventilation = "LOW-FLOW OXYGEN THERAPY" and date of discharge to non-hospitalized residence is missing or greater than date of assessment
3 - HOSPITALIZED, NO OXYGEN THERAPY	Date of assessment < date of discharge to non-hospitalized residence and Date of assessment > date of last oxygen usage
2 - NON-HOSPITALIZED, LIMITATION OF ACTIVITY	Date of assessment > date of discharge to non-hospitalized residence and participant has not been re-hospitalized and date of assessment > date of last oxygen usage and does not meet the classification for group 1.
1 - NON-HOSPITALIZED, NO LIMITATION OF ACTIVITY	Date of assessment > date of discharge to non-hospitalized residence and participant has not been re-hospitalized and date of assessment > date of last oxygen usage and last and subsequent recorded assessment is "1 - NON-HOSPITALIZED, NO LIMITATION OF ACTIVITY".

All non-Death derived values will be flagged in the dataset.

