5.4.1.8. Recovery or Improvement Relative to Baseline in SpO₂/FiO₂ Ratio

The ratio of SpO₂/FiO₂ will be calculated for each day using date-time matched values. Change from baseline in SpO₂/FiO₂ will be calculated as average of the daily

assessments, for participants who are not invasively mechanically ventilated. It will be analysed using a composite strategy to handle the intercurrent events as described in the individual endpoint sections. If a participant is a non-responder due to an intercurrent event for either SpO₂ or FiO₂ then they will be a non-responder for the ratio.

Participants will meet the endpoint if they have an improvement relative to baseline in SpO₂/FiO₂ ratio (derived where higher values indicate improvement) or they have recovered (the participant is discharged from investigator site for any other reason other than advanced facilitated care or the participant is independent from supplementary oxygen and SpO₂ is missing).

5.4.1.9. Oxygen-free Days up to Day 28

A participant is considered oxygen free on a day if they meet the definition in Section [5.3.1.5](#).

Intermittent data is expected after discharge from investigator site, therefore if participants have discontinued oxygen and have been discharged to a non hospitalised residence, they will be considered to be oxygen-free during the intermittent timepoints.

5.4.1.10. Ventilator-free Days up to Day 28

A participant is considered ventilator-free on a day if they meet the definition for being alive and not invasively mechanically ventilated in Section [5.4.1.3](#).

Intermittent data is expected after discharge from investigator site, therefore if participants have discontinued ventilation and have been discharged to a non hospitalised residence, they will be considered to be ventilation-free during the intermittent timepoints.

5.4.1.11. Time to Resolution of Pyrexia (>48h) up to Day 28

Time from dosing (days) to first resolution of pyrexia (defined as the first day of a >48-hour period with temperature below thresholds below) up to (and including) Day 28:

Location	Pyrexia Threshold	Core Temperature Equivalent
Forehead	>36.3°C	>37.8°C
Axilla	>36.6°C	>37.8°C
Sublingual region	>37.2°C	>37.8°C
Rectum or Tympanic membrane	>37.8°C	>37.8°C
Pulmonary artery branch	>37.8°C	>37.8°C
Bladder	>37.8°C	>37.8°C
Esophagus	>37.8°C	>37.8°C
Nasopharynx	>37.8°C	>37.8°C
Brain	>37.8°C	>37.8°C
Other	>36.3°C (Minimum Pyrexia Threshold)	>37.8°C

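### Part 2 ventilator-free days omit the condition of being alive, so days after death score as ventilator-free; separately, SAP 4.4.1.1 applies a Day 28 death rule at Days 4, 7 and 14

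*SAP*

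**What the plan says.** **Ventilator-free days.** Part 2 SAP 4.4.1.7 reads: "A participant is considered ventilator-free on a day if they are not using invasive mechanical ventilation as derived from the worst case ventilation record". It adds a rule for gaps after discharge but none for death. The count goes into a negative binomial regression (4.4.2.3).

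The record it relies on is built in Part 2 SAP 6.3.2.1:

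- Status is derived for Days 1 to 60. Invasive mechanical ventilation (IMV) is code 5 and Death is code 6.
- On missing status: "Ventilation status will only be missing after last contact for subjects who have withdrawn from the trial".
- On log handling: "Ventilation statuses with missing end-dates will be assumed ongoing", and "participants with no open ventilation logs will be assumed to have Ventilation=None".

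Protocol 4.4 counts a participant as a completer if they have "completed all visits of the study through to Day 60 or has died prior to Day 60", so a death is not a withdrawal.

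Three other places handle death explicitly:

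- Part 1 SAP 5.4.1.10 counts a ventilator-free day only "if they meet the definition for being alive and not invasively mechanically ventilated".
- Part 2 SAP 4.4.1.4 says: "Participants will meet the endpoint if they are alive and not requiring invasive mechanical ventilation at Day 7, 14, 28, 42 and 60".
- Part 2 SAP 6.3.2.2 has clinical status "recorded as 8-Death from date of death to Day 60 inclusive, this will override any collected clinical status". Section 6.3.2.1 has no equivalent sentence for ventilation status.

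**IMV up to Day 28.** Part 2 SAP 4.4.1.1 evaluates initiation of IMV up to each of Days 4, 7, 14 and 28. Its single death rule counts as an event any death by Day 28 without IMV. Section 4.4.1.2 ties its death rule to the day being analysed, and 4.4.1.3 places the event at the time of death. The Part 1 version (5.4.1.1) had only the Day 28 timepoint, where the same rule is consistent.

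**The concern.** A dead participant is not using a ventilator. Without a condition of being alive, the more days that follow a death within the 28-day window, the higher the ventilator-free count. An early un-intubated death earns the maximum score, and a death on the ventilator can outscore a survivor who was weaned late. If otilimab lowers mortality, the placebo arm is credited with more post-death days, so the benefit on this endpoint is understated and could reverse.

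Deaths will not be rare. Protocol 2.2.2 cites UK 28-day mortality of 55% at ages 70-79 and 65% at 80 and over, in figures given alongside ICU data. The Part 2 rate may differ, because non-ventilated patients are also enrolled.

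In 4.4.1.1 the problem is one of timing: later deaths count as events by Day 4, 7 or 14, before they have happened.

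**Working it through.** The plan states no figure that depends on this rule, so the check applies the written definitions day by day over Days 1 to 28.

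**1. Can post-death days drop out?** A post-death day could carry one of four statuses under 6.3.2.1:

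- Death (code 6): not IMV, so it counts.
- None (no open log): not IMV, so it counts.
- Missing: reserved for withdrawals, so it does not apply to deaths.
- IMV: only if an IMV log was left open at death and the Death code is not applied from the date of death. The day then does not count.

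Section 4.1.4 does not help. It promises a strategy within each endpoint definition and otherwise defaults to treatment policy; 4.4.1.7 gives none.

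**2. Scores for hypothetical participants**

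| Participant | As written | Alive required |
|---|---|---|
| Never on IMV, survives | 28 | 28 |
| Never on IMV, dies Day 5 | 28 under every coding | 4 (Days 1-4) |
| IMV from Day 1, dies Day 10; later days None, log closed | 28 − 10 = 18 | 0 |
| Same; Death coded from Day 10, log closed or open | 28 − 9 = 19 | 0 |
| Same; later days not coded Death, log open | 0 | 0 |
| IMV Days 1-20, survives | 28 − 20 = 8 | 8 |

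**3. Effect on the treatment difference.** For a death on day d with the log closed, the two rules differ by 28 − d days if that day is scored as IMV. They differ by 29 − d if the participant was not on IMV or the day is coded Death. If death timing is the same in both arms:

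understatement of the difference in means = absolute mortality reduction × mean credited days per death

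The documents do not give a mean death day, so a range of 8 to 16 is assumed:

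- 10-point reduction: 0.10 × (28 − 16) = 1.2 to 0.10 × (29 − 8) = 2.1 days.
- 15-point reduction: 0.15 × 12 = 1.8 to 0.15 × 21 = 3.15 days.

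A second set of assumptions spreads deaths evenly and credits 29 − d days per death. Over Days 2-28 the mean credit is 14 days, giving 1.4 for a 10-point reduction; over Days 2-14 it is 21 days, giving 2.1.

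A simulation with 400,000 per arm used only assumed inputs: mortality 45% versus 35%, mean death day about 12, 30% or 70% of deaths un-intubated, and mean survivor IMV duration of 4, 8 or 14 days.

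- Difference as written: −1.02 to +0.48 days.
- Difference with alive required: +0.60 to +2.08 days.
- Gap between the rules: 1.57 to 1.64 days (the formula gives 1.59 to 1.63).

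The gap is stable, but the sign of the as-written difference depends on the inputs.

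**4. Oxygen-free days (4.4.1.6).** This rule requires Ventilation=None. For a participant on oxygen Days 1-5 who dies on Day 5 with the log closed, the score is 28 − 5 = 23 if later days are set to None and 0 if they are coded Death. This endpoint is affected only under the first coding.

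**5. Section 4.4.1.1.** An un-intubated death on Day 20 is an event up to Days 4, 7, 14 and 28 as written; 4.4.1.3 places it at Day 20. The over-count at Day t is the share of participants not on IMV at baseline who die un-intubated from Day t+1 to Day 28. As an illustration, assume 10% to 30% die un-intubated by Day 28, evenly over the 27 days from Day 2:

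| Day t | Share of these deaths after Day t | Over-count (percentage points) |
|---|---|---|
| 4 | 24/27 | 8.9 to 26.7 |
| 7 | 21/27 | 7.8 to 23.3 |
| 14 | 14/27 | 5.2 to 15.6 |
| 28 | 0 | 0 |

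**The case against.** No sentence in the SAP says that days after death are ventilator-free. That follows from the literal rule and the coding. Death sits above IMV in the code list, and a programmer could treat it as worse than IMV and exclude it. The Output and Programming Specification, to which the SAP defers data-handling detail, may do so. This stands as a limit: the finding concerns the SAP text, not what was programmed. But no rule in the SAP excludes code 6.

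The dependence on open logs disappears if Death is carried forward from the date of death, arguably the more natural reading. Both that point and the oxygen-free one are therefore conditional. The main point is not: a never-ventilated death on Day 5 scores 28 under every coding.

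The size in days rests on assumed death timing and is a difference in means, whereas the planned model estimates a ratio. That is fair. The range describes the summary statistics and is not a forecast of the model result.

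The two parts have separate analysis plans, so departing from the Part 1 definition is not in itself a contradiction. However, Part 2 treats death unfavourably in 4.4.1.1 to 4.4.1.3, 4.4.1.5 and 4.4.1.8, and nothing explains a different choice here, so an oversight is the likelier explanation.

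On 4.4.1.1, the heading refers to Day 28 and the death rule is right for that day. The fault is confined to Days 4, 7 and 14.

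**Conclusion.** Both points hold on the SAP as written. Section 4.4.1.7, followed literally, credits days after death as ventilator-free. With equal death timing in the two arms, a mean death day of 8 to 16 and logs closed at death, this understates each 10-point mortality reduction by about 1.2 to 2.1 mean ventilator-free days. Whether the observed difference shrinks or reverses cannot be settled from the documents. Section 4.4.1.1 over-counts events at Days 4, 7 and 14 by the share of later un-intubated deaths; its Day 28 result is correct.

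The reach is limited. These endpoints are exploratory and outside the testing hierarchy. The primary endpoint, the mortality endpoints, the sample size and type I error are unaffected. The definitions should still be corrected, because they change the computed values and 4.4.1.7 scores death as a favourable outcome.

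**What to change.** - **4.4.1.7:** define a ventilator-free day as one on which the participant is alive and not on IMV, with the day of death and every later day counting as 0.
- **6.3.2.1:** state that ventilation status is Death from the date of death onward, overriding both None and any open log, in line with the clinical-status rule in 6.3.2.2. This also settles oxygen-free days in 4.4.1.6 and removes any dependence on whether a site closed its log.
- **4.4.1.1:** replace the fixed Day 28 cut-off in the death rule with the day being analysed, as 4.4.1.2 already does.

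The cost is SAP wording and matching programming. No new data are needed.

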4.4.1.10. Oxygen Use Following Discharge to Non-hospitalized Residence

The number of participants will be presented for the following categories:

- Not discharged to non-hospitalized residence or death
- Discharged to non-hospitalized residence and used oxygen post-discharge

- Discharged to non-hospitalized residence and did not use oxygen post-discharge.

In addition, for participants discharged to a non-hospitalized residence and for oxygen usage post-discharge, the number of days on oxygen will be summarized for each participant for the following:

- 1-< 7 days
- 7- <14 days
- \geq 14 days.

Summary statistics for the number of days of oxygen use, including mean, median (IQR), min and max will also be provided.

4.4.1.11. Time to Improvement of at Least 2 Categories Relative to Baseline in Clinical Status up to Day 60

Time from dosing (days) to final improvement of at least 2 categories relative to baseline in clinical status (see [Table 2](#)) up to (and including) Day 60. Evaluated for all participants with clinical status greater than 2 at baseline.

Note: if a participant has an improvement of at least 2 categories relative to baseline but then progresses back to a less than 2 category improvement the participant has not had their final improvement of at least 2 categories.

This endpoint will use a composite approach such that if the event has not occurred prior to the intercurrent event of death (on or prior to Day 60), then time will be censored at the end of follow-up (Day 60).

4.4.1.12. Number of Days in Each Category of Clinical Status up to Day 60

For each participant, the number of days in each clinical status (see [Table 2](#)) or missing will be calculated up to (and including) Day 60.

The median number of days in each category will be presented overall. a participant's final outcome (Alive vs Dead or Withdrawn)

4.4.1.13. Change in COVID-19 Signs and Symptoms up to Day 60

Participants change in COVID-19 signs and symptoms at Day 4, 7, 14, 28, 42 and 60 relative to baseline will be analysed. Participants will be absent of a symptom if they had a symptom at baseline and the symptom was not present at the timepoint of interest. This endpoint will use a composite approach for death or initiation of invasive mechanical ventilation, such that participants who die prior to or are using invasive mechanical ventilation on the day of interest (and so cannot have symptoms recorded), will be considered to still have the symptom.

Unadjusted relative risks, risk differences and odds ratios will be calculated and presented with 95% confidence intervals. For odds ratios, if the proportions are below 2% in any treatment group then exact 95% confidence interval will be calculated by inverting two one-sided (equal tail) exact tests that are based on the noncentral

hypergeometric distribution. All other confidence intervals will use the Wald method. A 2-sided Fisher's Exact Test will be performed, and p-values will be presented.

4.4.1.14. Post-Baseline Glucocorticoid Use up to Day 60

Post-Baseline glucocorticoid use is defined such that participants who required glucocorticoid use on a day if their concomitant medications include glucocorticoids on that day, where glucocorticoids for COVID-19 were defined prior to DBF. A missing stop date for any glucocorticoids has been assumed to be the minimum of last contact, end of study and Day 60.

Summaries up to Day 60 will be provided on the duration of post-Baseline glucocorticoid use, overall and separately for participants that have died or withdrew, and those that completed the study. This will include counts and proportions of participants with post-Baseline glucocorticoid use of 0 days, 1-<7 days, 7-<14 days and ≥ 14 days

4.4.2. Main Analytical Approach

4.4.2.1. Time to Event Endpoints

The following exploratory endpoints will be analysed using time to event analyses with a follow-up to Day 28:

- Time to invasive mechanical ventilation (if not previously initiated)
- Time to definitive extubation

The following exploratory endpoints will be analysed using time to event analyses with a follow-up to Day 60:

- Time to improvement of at least 2 categories relative to baseline on an ordinal scale

The endpoints will be analysed as per Section [4.3.2.2](#)

These time to event endpoints may also be derived using additional follow-up times to support future sensitivity analyses.

4.4.2.2. Binary Endpoints

The following exploratory endpoints will be analysed as binary endpoints:

- Invasive mechanical ventilation (if not previously initiated)
- Alive and not invasively mechanically ventilated

Binary secondary endpoints will be analysed as per Section [4.2.2](#).

In addition, the following will be produced:

- A table and stacked bar chart of the counts and proportion of participants in each ventilation status at each visit.

- A summary of duration of invasive mechanical ventilation will be produced, using descriptive statistics and counts and proportion of participants who have 1- < 7 days, 7- < 14 days, \geq 14 days use.

4.4.2.3. Count Endpoints

The following exploratory endpoints will be analysed as count data

- Oxygen-free days
- Ventilator-free days

Summary statistics of the number of days will be presented and the data will be analysed using negative binomial regression adjusting for covariates as per Section 4.1.1.

4.4.2.4. Continuous Endpoints

The following exploratory endpoints will be analysed as continuous endpoints:

- Change from Baseline in FiO_2

Continuous endpoints will be summarised using the trimmed means approach (Permutt, 2017) where the proportion of data to be trimmed will be determined by the amount of missing data due to intercurrent events as defined in Section 4.1.4.

Study withdrawal will be treated as a negative event if it occurs prior to one of the listed intercurrent events. If the subject has recovered (has one of the intercurrent events listed within the endpoint definition) prior to withdrawal then they will be considered to be recovered post-withdrawal.

Missing data without reason (no accompanying intercurrent event or withdrawal) will be treated as missing at random and will not count towards the trimmed sample.

A plot of the change from baseline using the trimmed sample will be generated.

